BMI	body mass index
bpm	Beats per minute
BRV	brivaracetam
BUN	blood urea nitrogen
CHMP	Committee for Medicinal Products for Human Use
CR CL	creatinine clearance
CRF	case report form
C-SSRS	Columbia-Suicide Severity Rating Scale
DBP	diastolic blood pressure
ECG	electrocardiogram
EDV	Early Discontinuation Visit
ER	emergency room
EU	European Union
F	Female
FDA	Food and Drug Administration
FEV	Full Evaluation Visit
FV	Final Visit
GGT	Gamma-glutamyl transpeptidase
HADS	Hospital Anxiety and Depression Scale
HDL	High-density lipoprotein
HRQoL	Health-Related Quality of Life
ILAE	International League Against Epilepsy
LDL	low-density lipoprotein
MedDRA	Medical Dictionary for Regulatory Activities
M	Male
MEV	Minimal Evaluation Visit
N/A	Not applicable
PBO	placebo
PCST	potentially clinically significant treatment-emergent
PGS	primary generalized seizures
POS	partial onset seizure
PT	preferred term
QOLIE-31-P	Patient Weighted Quality of Life in Epilepsy Questionnaire
RBC	Red Blood Cell
SAE	serious adverse event

SAP	statistical analysis plan
SBP	systolic blood pressure
SD	standard deviation
SGOT	serum glutamic oxaloacetic transaminase
SGPT	serum glutamic pyruvic transaminase
SOC	system organ class
TEAE	treatment-emergent adverse event
ULN	Upper Limit of Normal
V	Visit
VAS	visual analog scale
WBC	White Blood Cell
WHO-DRL	World Health Organization Drug Reference List
YEV	Yearly Evaluation Visit

REDACTED COPY
This document cannot be used to support any marketing authorization application and any extensions or variations thereof.

1 INTRODUCTION

This statistical analysis plan (SAP) defines the scope of statistical analyses and provides a detailed description of statistical methodology for the statistical analyses to support the final clinical study report for N01379.

2 PROTOCOL SUMMARY

2.1 Study objectives

2.1.1 Primary objective

To evaluate the long-term safety and tolerability of brivaracetam (BRV) at individualized doses with a maximum of 200mg/day in subjects suffering from epilepsy

2.1.2 Secondary objective

To evaluate the maintenance of efficacy over time of BRV (for subjects with partial onset seizures [POS] and subjects with primary generalized seizures [PGS])

2.1.3 Exploratory objectives

Exploratory objectives for subjects with POS/PGS:

- To explore the effects of BRV on subjects' Health-Related Quality of Life (HRQoL)
- To explore direct medical resource use
- To explore any change in socio-professional status
- To assess the role of gene variants of synaptic vesicle protein 2 (SV2) in affecting response to BRV (as part of a DNA analysis at the program level)

2.2 Study variables

2.2.1 Safety variables

2.2.1.1 Primary safety variables

- Occurrence of a treatment-emergent adverse event (TEAE)
- Withdrawal due to adverse event (AE)
- Occurrence of a serious adverse event (SAE)

2.2.1.2 Other safety variables

- Laboratory tests (blood chemistry, hematology, urinalysis, and endocrinology)
- Vital signs (systolic blood pressure [SBP], diastolic blood pressure [DBP], pulse rate) and body weight
- Electrocardiogram (ECG)
- Physical and neurological examinations

- Change in Hospital Anxiety and Depression Scale (HADS) scores from the Baseline of the previous study to each assessment for the first 2 years and to the last Evaluation Period assessment during the first 2 years

2.2.2 Efficacy variables

2.2.2.1 Secondary efficacy variables

For subjects with focal-onset epilepsy:

- POS (type I) frequency per 28 days during the Evaluation Period
- Percent reduction in POS (type I) frequency per 28 days from Baseline of the previous study to the Evaluation Period
- Responder rate for POS (type I) frequency over the Evaluation Period. A responder is defined as a subject with a $\geq 50\%$ reduction in seizure frequency from the Baseline Period of the previous study

No secondary efficacy variables are defined for subjects with generalized epilepsy

2.2.2.2 Other efficacy variables

For subjects with focal-onset epilepsy:

- Percentage of subjects continuously seizure-free for all seizure types (I+II+III) for at least 6 months and at least 12 months during the Evaluation Period

For subjects with generalized epilepsy:

- Generalized (type II) seizure days per 28 days during the Evaluation Period
- Percent reduction in generalized (type II) seizure days per 28 days from Baseline of the previous study to the Evaluation Period
- Responder rate for generalized (type II) seizure days over the Evaluation Period. A responder is defined as a subject with a $\geq 50\%$ reduction in seizure days from the Baseline Period of the previous study.
- Percentage of subjects continuously seizure-free for all seizure types (I+II+III) for at least 6 months and at least 12 months during the Evaluation Period

The following will be evaluated separately for subjects with focal-onset epilepsy and subjects with generalized epilepsy:

- Change in Patient Weighted Quality of Life in Epilepsy Questionnaire (QOLIE-31-P) scores from Baseline of the previous study to each assessment for the first 2 years and to the last Evaluation Period assessment during the first 2 years

2.2.2.3 Pharmacoeconomic variables

Due to the inconsistencies in data captured and collection forms across LTFU studies, the following variables will be provided in subject data listings only, but will not be evaluated or descriptive summarized:

- Direct costs (healthcare provider consultations not foreseen by the protocol, concurrent medical procedures, concomitant medications, hospitalizations, and emergency room [ER] visits) during the first 2 years of the Evaluation Period
- Socio-professional data for each assessment for the first 2 years and for the last assessment during the first 2 years of the Evaluation Period

2.3 Study Design and Conduct

This is an open-label, long-term follow-up, multicenter, noncomparative, single-arm study of BRV. The primary objective is to evaluate the long-term safety and tolerability of BRV at individualized doses up to a maximum of 200mg/day in subjects with epilepsy. The secondary objective is to evaluate the maintenance of efficacy of BRV. Exploratory objectives are to assess the effects of BRV on subjects' HRQoL, obtain information on the direct costs, explore changes in socio-professional status, and assess the role of gene variants of SV2. DNA analysis will only be done for those subjects coming from N01358.

Study N01379 enrolled subjects 16 years of age and older who had completed N01358 or N01258. Study N01358 enrolled subjects with refractory partial onset seizures (POS) whether or not secondarily generalized and N01258 enrolled subjects with localization-related or generalized epilepsy (designated as "PGS subjects").

Subjects from N01258 were started at an oral dose of BRV 200mg/day (2 equally divided doses administered twice daily) and should be maintained at this dose for at least 2 weeks unless the subject is unable to tolerate treatment. Subjects from N01358 were started on oral BRV at a dose of 150mg/day (2 equally divided doses administered twice daily) at study entry and should be maintained at this dose for at least 2 weeks unless the subject was unable to tolerate treatment.

Subjects who enroll in the study entered an Evaluation Period during which treatment with BRV was initiated. The dose of BRV can be adjusted based on the individual subject's seizure control and tolerability. Dose increases can be made in increments of 50mg/day on a weekly basis up to a maximum of 200mg/day; dose decreases can be made in steps of 50mg/day on a weekly basis. Subjects who discontinue treatment with BRV enter a Down-Titration Period during which the dose of BRV is decreased in steps of 50mg/day on a weekly basis with a last down-titration step at 20mg/day for 1 week. Subjects who have completed the Down-Titration Period or subjects who discontinue during the Evaluation Period without entering the Down-Titration Period enter a Post-Treatment Period for a minimum of 2 weeks and a maximum of 4 weeks.

The maximum allowable daily dose for this study is 200mg/day based on the protocol. It is recommended that the daily dose be administered in 2 equal intakes.

Dose adjustment to concomitant AEDs may be made at any time during the study and subjects may start new AEDs. Concomitant AEDs may also be discontinued.

The visit schedule for this study is the same without regard to the subject's previous study. Study visits at Months 2, 6, 12, 18, 24, and so forth are either Full Evaluation Visits (FEVs)

or Yearly Evaluation Visits (YEVs) at which a greater number of assessments are performed. Study visits at Months 1, 3, 9, 15, 21, and so forth are Minimal Evaluation Visits (MEVs). In addition, a phone call is scheduled at the end of the Down-Titration Period and a Drug-Free Final Visit (FV) is scheduled at the end of the Post-Treatment Period. The study schedule, as just described, is shown in Table 2-1.

Table 2-1: Study Schedule

1st Year Follow-up		
Month	Visit	Type of Visit
M0	V1	Entry Visit (EV)
M1	V2	MEV
M2	V3	FEV
M3	V4	MEV
M4		
M5		
M6	V5	FEV
M7		
M8		
M9	V6	MEV
M10		
M11		
2nd and subsequent years follow-up		
M12	V7	YEV
M15	V8	MEV1
M18	V9	FEV
M21	V10	MEV2
...

FEV=Full Evaluation Visit; MEV=Minimal Evaluation Visit; M=month, V=Visit, YEV=Yearly Evaluation Visit

All subjects should have a Visit 1 at the start of N01379. Visit 1 will correspond to the last visit from the previous study and should be the visit at which study drug is dispensed for N01379.

This study will run throughout the duration of the clinical development period of brivaracetam, and will continue until a marketing authorization is granted by any Health Authority in an indication for the adjunctive treatment in adults with refractory POS, whether or not secondarily generalized, until the Sponsor decides to close the study, until a managed access program, named patient program, compassionate use program, or similar type of access program is established as allowed per country-specific requirement in addition to legal and regulatory guidelines, or until brivaracetam development is stopped by the Sponsor.

2.4 Determination of Sample Size

No sample size calculation was done. Sample size was dependent upon recruitment into and completion of preceding studies.

3 DATA ANALYSIS CONSIDERATIONS

3.1 General presentation of summaries and analyses

Statistical analysis and generation of tables, figures, subject data listings, and statistical output will be carried out using SAS® Version 9.1 or higher.

Descriptive statistics, such as the mean, standard deviation (SD), median, 25th percentile, 75th percentile, minimum value, and maximum value for quantitative variables, and counts and percentages for categorical variables, will be provided. Denominators for percentages will generally be based on the set of subjects with at least 1 assessment at the time point or at least 1 assessment during the time interval being summarized.

All summaries will be descriptive; no statistical hypothesis testing is planned.

Unless otherwise noted, summaries will present BRV overall, which will include all subjects exposed to BRV during the study.

Subject data listings will be provided and will present source data and key derived variables for statistical analyses.

3.2 Analysis time points

3.2.1 First and last dose of BRV

Unless otherwise noted, all references to the first dose of BRV in this SAP refer to the first dose of BRV during N01379 (ie, not the first dose of BRV from the previous study in which subjects participated in prior to N01379). Unless otherwise noted, all references to the last known dose of BRV in this SAP refer to the last dose of BRV taken across any study periods (ie, not necessarily the last dose of BRV during the Evaluation Period).

3.2.2 Relative day

Relative day will be calculated with Day 1 representing the day of first dose of BRV, the previous day is Day -1 and each day prior to that is Day -2, Day -3, etc. Subsequent relative days to Day 1 will be Day 2, Day 3, etc. For days after the last dose of BRV, relative day will be calculated as the current date minus the date of last dose of BRV and including a '+' to denote post treatment days (eg, the day after the last dose of BRV will be Day +1). Relative day will not be calculated for partial or missing dates.

3.2.3 Study Entry Visit

The study Entry Visit (EV) corresponds to assessments performed at the time of entry into N01379. Subjects will not have any interruption in study drug dosing during the transition to N01379. Selected assessments from the following visits from the previous study will be summarized at EV:

Study	Visit (Time Point)
N01258	Visit 7 (at Week 2)
N01358	Visit 7 (at Week 20)

The following assessments are to be performed for all subjects at the above time points: laboratory parameters, vital signs, and ECGs; the results for these assessments will be summarized at EV. For study N01258, the following selected assessments will be used for summary at EV for laboratory parameters, vital signs, and ECGs

Assessment	Visit (Time Point)
Laboratory	Laboratory assessment done on AM at Visit 7
Vital signs	60 minutes after IV dose on AM at Visit 7
ECGs	12 hours after IV dose on AM at Visit 7

Body weight is not recorded at Visit 1 for N01379. The body weight recorded at the above study visits for the previous studies will be summarized for EV.

3.2.4 Study periods

The Baseline Period for N01379 corresponds to the Baseline Period of the previous studies, and is defined for seizure outcomes and direct cost parameters. The Baseline Period is defined as study days on or after the date of Visit 1 and prior to the date of Visit 2 for N01258 and study days on or after the date of Visit 1 and prior to the date of Visit 3 for N01358.

The study is divided into 3 periods: Evaluation Period, Down-Titration Period, and Post-Treatment Period. A subject is classified as “discontinued” if the subject has a termination case report form (CRF) or has an early discontinuation visit (EDV). A subject is classified as “completed” if this subject completes the full extent of the study as defined in the protocol at database lock.

A “discontinued” subject can be potentially slotted into the 3 periods of the study. The following algorithms will be used to slot the subject appropriately into the Evaluation Period, Down-Titration Period, and Post-Treatment Period.

- For Evaluation Period, the start date is the date of first dose of BRV, and the following algorithm is used to determine the end date:
 - If the subject enters the Down-Titration Period, then the date of EDV is the end date;
 - If the subject does not enter the Down-Titration Period but meets 1 of the following criteria, the Evaluation Period ends on date of last dose of BRV:
 - Without an EDV but having a termination CRF,
 - With an EDV and having a termination CRF,
 - With an EDV and the date of EDV prior to the database lock date and having no termination CRF.

- A subject is considered entering Down-Titration Period only if the subject has an EDV and at least 1 dose of study drug after the date of EDV, the start date of Down-Titration Period is set as 1 day after the date of EDV, and the Down-Titration Period ends on date of last dose of BRV. A subject without an EDV but having a termination CRF or with an EDV but without any dosing of study drug after the EDV will not have the Down-Titration Period, and no artificial Down-Titration Period will be created for analysis.
- A subject is considered entering the Post-Treatment Period if the subject has at least 1 contact (scheduled visit, unscheduled visit, or telephone contact) after the date of last dose of BRV. The Post-Treatment Period starts 1 day after date of last dose of BRV irrespective of entering the Down-Titration Period, and there is no end date.

A “completed” subject can potentially have Evaluation Period, Down-Titration Period, and Post-Treatment Period. At the time of study termination by the Sponsor, subjects will discontinue the study drug following the down titration process or will be converted without titration to commercial BRV where available; alternatively, subjects may be initiated without down-titration in a managed access program, named patient program, compassionate use program, or similar type of access program as allowed per country specific requirements in addition to legal and regulatory guidelines.

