5.1.1 Study duration per subject

Subject recruitment for the study will begin in approximately Q2 2011. For each subject, the study will last from study entry until either regulatory approval of BRV has been granted by any Health Authority in an indication of adjunctive treatment of POS, until the Sponsor decides to close the study; until subjects transition to another BRV study; until a managed access program, named patient program, compassionate use program, or similar type of access program is established as allowed per country-specific requirement in addition to legal and regulatory guidelines; or until BRV development is stopped by the Sponsor.

The following study periods are defined:

- Evaluation Period (Visit 1 until the Last Evaluation Period Visit or Early Discontinuation Visit [EDV]): Subjects who enroll in N01379 will immediately enter the Evaluation Period.
- Down-Titration Period (up to 4 weeks)
 - If the subject is discontinuing study drug, the Investigator will first plan an EDV followed by the progressive down-titration of study drug.
 - During the Down-Titration Period, the BRV dose may be decreased in steps of a maximum of 50mg/day on a weekly basis. A last down-titration step at 20mg/day for 1 week should be included prior to the Posttreatment Period.
- Posttreatment Period (2 to 4 weeks): After completion of the Down-Titration Period, or for those subjects who for extenuating circumstances do not complete a Down-Titration Period, the subject will be required to enter a Posttreatment Period for a minimum of 2 weeks and a maximum of 4 weeks, followed by a Final Visit (FV).
- The end of the study is defined as the date of the last visit of the last subject in the study.

For subjects who transition to another BRV study or a managed access program or similar type of program or who will be converted to commercial BRV if, when, and where available, the Down-Titration Period and FV are not applicable.

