	Entry Visit (EV)	Full Evaluation Visit (FEV)	Minimal Evaluation Visit (MEV)	Yearly Evaluation Visit (YEV)	Last Evaluation Period Visit (or Early Discontinuation Visit [EDV])	Down-Titration Phone Call (DTP) ^a	Final Visit (FV)	Reference to Section
Visit	V1	V3, V5, V9...	V2, V4, V6, V8, V10...	V7...	NA	NA	NA	5.3
Month	M0	M2, M6, M18...	M1, M3, M9, M15, M21...	M12...	NA	NA	NA	5.3

leaving the study at the end of the program (completed subjects). Alternatively, end of study status will be completed at the EDV for subjects who may transition into another BRV study, or be initiated without down-titration in a managed access program, named patient program, compassionate use program, or similar type of access program as allowed per country-specific legal and regulatory requirements, or for subjects who will be converted without down-titration to commercial BRV if, when, and where available.

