8.6 Last Evaluation Period Visit or Early Discontinuation Visit

For subjects who transition to another BRV study or a managed access program or similar type of program or who convert to commercial BRV (if, when, and where available), the EDV will need to be completed; however, down-titration and FV are not applicable.

- QOLIE-31-P (if the EDV occurs within the first 2 years)
- HADS (if the EDV occurs within the first 2 years)
- Vital signs
- Weight
- Physical examination
- Neurological examination
- ECG
- IVRS call
- DRC dispensed (if applicable; DRC not dispensed if subject will not down-titrate)
- DRC retrieved
- Recording of seizures
- Hospital stays (if the EDV occurs within the first 2 years)

- Suicidality assessment (C-SSRS)
- Healthcare provider consultations not foreseen by the protocol (if the EDV occurs within the first 2 years)
- Socio-professional data (if the EDV occurs within the first 2 years)
- Laboratory safety assessments: hematology, blood chemistry, urinalysis, and urine pregnancy test (if applicable)
- Recording of AEs
- Medical procedures
- Concomitant AED
- Concomitant non-AED
- Drug dispensing (if applicable; drug not dispensed if subject will not down-titrate)
- Drug return/accountability
- End of study status (if the subject will not down-titrate)

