5 STUDY POPULATION CHARACTERISTICS

5.1 Subject disposition

Due to differences in data format across studies, in order to facilitate summary of subject disposition, the reasons for discontinuation for individual studies will be collapsed as follows for summaries:

LTFU Category	CRF Reason
ADVERSE EVENT	ADVERSE EVENT
LACK OF EFFICACY	LACK OF EFFICACY
	LOSS OF EFFICACY
LOST TO FOLLOW-UP	LOST TO FOLLOW-UP
SUBJECT CHOICE	CONSENT WITHDRAWN
	WITHDRAWAL OF CONSENT FOR PERSONAL REASONS NOT RELATED TO AES
	WITHDRAWAL OF CONSENT FOR PERSONAL REASONS NOT RELATED TO AES OR LACK OF EFFICACY
OTHER	PROTOCOL VIOLATION
	OTHER REASON
	OTHER
MISSING	If subject discontinued the study and the termination CRF is not available

Only 1 primary reason for discontinuation should have been reported. In the event that more than 1 reason is specified in the clinical database, both reasons will be summarized and a footnote will be added to the summary table to indicate that at least 1 subject is counted for multiple reasons for discontinuation.

An overall summary of disposition will be provided for all enrolled subjects (ie, all subjects who signed informed consent). The following will be summarized:

- The number of subjects in the Safety Analysis Set
- The number of subjects excluded from the Safety Analysis Set
- The number of subjects completed the study
- The number of subjects discontinued from the study, including the reason for discontinuation. If subject discontinued the study and the termination CRF is not available, the reason for discontinuation will be reported as “MISSING”.

Additionally, an overall summary of disposition will present the following for subjects in the Safety Analysis Set:

- The number of subjects completed the study
- The overall number of subjects discontinued and the number of subjects discontinued by primary reason for discontinuation. If subject discontinued the study and the termination CRF is not available, the reason for discontinuation will be reported as “MISSING”.

Overall subject disposition will also be summarized by geographic region and seizure type for the Safety Analysis Set.

The number of subjects within each geographic region and the number of subjects within each seizure type will be summarized for the Safety Analysis Set.

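### SAP 3.2.4 counts planned exits with an EDV as discontinuations although they also fit its completed class, so late Kaplan-Meier retention has two possible answers

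*SAP*

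**What the plan says.** SAP 3.2.4 sets two classes. A subject is *discontinued* "if the subject has a termination case report form (CRF) or has an early discontinuation visit (EDV"; either limb is enough and no exception is made. A subject is *completed* if the subject "completes the full extent of the study as defined in the protocol at database lock". The algorithm for period end dates that follows is written for discontinued subjects only.

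Protocol 8.6 deals with subjects who move to another BRV study, a managed access or similar programme, or commercial BRV. For them, "the EDV will need to be completed; however, down-titration and FV are not applicable". Footnote m to Protocol Table 5-1 agrees: "end of study status will be completed at the EDV for subjects who may transition into another BRV study", and it treats access programmes and commercial conversion the same way.

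Protocol 5.1.1 defines how long the study lasts for each subject. After regulatory approval, its list of end points continues "until the Sponsor decides to close the study; until subjects transition to another BRV study; until a managed access program" and closes with the end of BRV development. The SAP's own list, in 2.3, reads "until the Sponsor decides to close the study, until a managed access program, named patient program" at the same place, so transfer to another BRV study has dropped out.

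The SAP 3.2.4 paragraph on completed subjects says: "At the time of study termination by the Sponsor, subjects will discontinue the study drug following the down titration process", or they convert to commercial BRV or enter an access programme.

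SAP 5.1 uses the classes. It reports the number of completers and "The overall number of subjects discontinued and the number of subjects discontinued by primary reason for discontinuation". It also gives Kaplan-Meier estimates of the percentage still on treatment at 3, 6, 12, 24, 36, 48 and 60 months. Permanently discontinued subjects are events on the last day of study drug; completers are censored on that day. The table of discontinuation reasons has no row for transition.

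**The concern.** An EDV cannot tell a true discontinuation from a planned exit, because the protocol requires the visit in both cases. Read literally, the EDV limb puts a subject who leaves for another BRV study or an access programme, still taking BRV, among the discontinued. Read against Protocol 5.1.1, the same subject has reached a planned end of the study and is a completer. The SAP does not say which rule prevails.

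The classification decides whether the subject is a Kaplan-Meier event or is censored, and which disposition count the subject enters. Under the literal rule, retention at the later time points is understated and the exits would be reported as other or missing reasons. These are disposition summaries rather than listed primary variables. The primary objective, however, is long-term safety and tolerability, and the percentage still on drug at up to 60 months is likely to be read as evidence on it. Two programmers following this SAP could report different retention from the same database.

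**Working it through.** The plan contains no retention figure to reproduce. The check has two parts.

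**Part 1: the rules applied to each way of leaving.**

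| Way of leaving | EDV required? | Meets the EDV limb of *discontinued*? | Planned end under Protocol 5.1.1? |
|---|---|---|---|
| Stops drug (e.g. adverse event, lack of efficacy) | Yes (5.1.1) | Yes | No |
| Transfer to another BRV study | Yes (8.6) | Yes | Yes |
| Access programme | Yes (8.6) | Yes | Yes, once established |
| Commercial BRV | Yes (8.6) | Yes | Yes, through approval |

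The last three rows can meet both SAP definitions. The SAP 3.2.4 paragraph on completed subjects does not resolve this. It describes what happens when the sponsor terminates the study, states no precedence, and does not mention transfer to another BRV study. SAP 5.1 speaks of permanently discontinued subjects, but nothing in the SAP defines that phrase separately, so 3.2.4 is the only classification rule available.

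**Part 2: how far retention could move.**

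Inputs from the documents: a month is 30 days (SAP 3.2.5), so 48 months is 1440 days and 60 months is 1800 days; the last Kaplan-Meier time point is 60 months (SAP 5.1); planned size is 650 to 720 plus up to 100 subjects (Protocol 5.1.2).

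Inputs assumed, because the documents give none: a constant discontinuation hazard h of 0.10, 0.15 or 0.20 per year; a share p of subjects with a planned exit date spread evenly over days 1080 to 1800 (months 36 to 60); exit dates independent of discontinuation.

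Formulas:

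- Exits censored: S(t) = exp(−h × t / 365.25).
- Exits counted as events: S(t) × (1 − p × F(t)), where F(t) is the fraction of the exit window elapsed. At day 1800, F = 1.

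For h = 0.15: S(1800) = exp(−0.15 × 1800 / 365.25) = exp(−0.739) = 0.477. With p = 0.25, 0.477 × 0.75 = 0.358.

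Retention at 60 months:

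| h per year | Exits censored | p = 5% | p = 10% | p = 25% | p = 50% |
|---|---|---|---|---|---|
| 0.10 | 61.1% | 58.0% | 55.0% | 45.8% | 30.5% |
| 0.15 | 47.7% | 45.4% | 43.0% | 35.8% | 23.9% |
| 0.20 | 37.3% | 35.5% | 33.6% | 28.0% | 18.7% |

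At 48 months, h = 0.15 and p = 0.25: S(1440) = exp(−0.591) = 0.554, and F = (1440 − 1080) / 720 = 0.5. With exits as events, 0.554 × (1 − 0.25 × 0.5) = 0.484.

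Here p is the share with a planned exit *date*; some of these subjects discontinue first. The share who actually leave this way is p times the average of S over the window. With S(1080) = exp(−0.444) = 0.642, the average is (0.642 − 0.477) / (0.15 × 720 / 365.25) = 0.556. So p = 25% corresponds to 0.25 × 0.556 = 0.139, about 14% of enrolled subjects.

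A simulated Kaplan-Meier analysis at h = 0.15 and p = 0.25 gave 0.478 censored against 0.359 as events for both N = 650 and N = 820. A second simulation with other assumptions (N = 750, 10% discontinuing per year, 25% with exits spread over months 24 to 60) gave 58.5% against 43.7%. These confirm the arithmetic; they do not support the assumed rates.

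**The case against.** The best case against has five parts.

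*Intent.* The SAP paragraph on completed subjects mentions commercial conversion and access programmes at sponsor termination, which suggests that those exits were meant to count as completions. That is a fair reading, and it narrows the open group to earlier exits and transfers to another BRV study; p in the table can be read as the share in that group alone. It is not an operative rule, though, and if it states the intent, the EDV limb contradicts it.

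*Protocol labels.* Footnote m applies the label discontinued to subjects who had an EDV and down-titrated, and completed to those leaving at the end of the programme. Transitioning subjects come under a separate alternative. So the protocol does not call them discontinued, but it does not call them completed either.

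*Wording in SAP 5.1.* A subject who moves to commercial BRV without a break is not naturally described as permanently discontinued, and the Kaplan-Meier text cross-refers to the exposure section, not to 3.2.4. This is reasonable, but the SAP does not say it.

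*Consequence.* All summaries are descriptive. Exposure cohorts and adverse event intervals rest on dosing dates, and the primary variables do not use this classification. This stands and limits the severity. The sizes are also wholly assumed, and nothing in the documents supports p as high as 50%.

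*Censoring has its own assumption.* Subjects who continue BRV elsewhere may be those doing well, in which case censoring them is not neutral. This stands too. It is a reason to state the choice and report the number of such exits, not to leave the choice open.

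**Conclusion.** The concern holds. As written, the EDV limb counts planned exits on drug as discontinuations, while the completed definition can claim the same subjects, and no precedence is stated. Under the assumed rates, the choice moves 60-month retention by about 2 percentage points (h = 0.20, p = 5%: 37.3% against 35.5%) to about 31 (h = 0.10, p = 50%: 61.1% against 30.5%). The central illustration is 48% against 36%. Those figures rest on an assumed hazard, exit share, exit timing and independence. What does not depend on the rates is that the two readings agree before the first such exit and diverge after it, and that the completed and discontinued counts depend on the same choice. This should be fixed before database lock; it does not threaten the primary safety variables.

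The documents do not say whether the termination CRF is the same form as the protocol's end of study status, so no conclusion is drawn on that limb of the rule.

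**What to change.** - **SAP 3.2.4:** make the two classes mutually exclusive and base them on the recorded reason for leaving. *Completed/transitioned*: left through sponsor closure, approval, transfer to another BRV study, an access programme or conversion to commercial BRV, whether or not an EDV was done. *Discontinued*: any other reason. State that the period end-date algorithm also applies to transitioned subjects.
- **SAP 2.3 and the completed-subject paragraph of 3.2.4:** add transfer to another BRV study, to match Protocol 5.1.1.
- **SAP 5.1:** add a transition row to the disposition summary, and state that these subjects are censored at their last dose of study drug in the Kaplan-Meier analysis. This extends the SAP's existing rule for completers. Showing the number of such exits lets the reader judge how much the curve depends on censoring.

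The cost is SAP wording and derivation code. The documents show no coded transition reason, so free-text reasons may need review before lock. No extra subject visits are needed.
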